### Blood Sampling

Blood samples will be collected into pre-chilled 2.7 mL EDTA, 4.9 mL EDTA, 9 mL EDTA, 2.6 mL Heparin and 2.7 mL Fluoride monovettes. All monovettes will be centrifuged at 3500 rpm for 10 min at 4°C and the resultant plasma supernatant will be aliquoted into 2 mL micro tubes. The 2.7 mL EDTA monovettes will be pre-treated with PHMB, PBS and NaOH and after centrifugation, HCl will be added to prevent the degradation of acylated Ghrelin and the sample will be spun for a further 5 minutes. All samples will then be stored at -80°C until analysis.

School of Sport, Exercise and Health Sciences

Influence of High-fat Overfeeding on Circulating Hepatokine Concentrations: A Randomised Crossover Study

17th November 2017

OVEREAT Study Statistical Analysis Plan

The data collected will be analysed using the software package SPSS (SPSS Version 23, SPSS Inc., Chicago, IL) and an alpha value of $P < 0.05$ will be set to indicate statistical significance. Parametric assumptions will be checked using the Shapiro-Wilk test in order to confirm normal distribution of the data. Two-hour area under the curve (AUC) calculations for plasma glucose and insulin during the oral glucose tolerance tests will be performed using the trapezoidal method. Whole-body insulin sensitivity will be calculated using the Matsuda Insulin Sensitivity Index (ISI) equation:

$$\frac{10,000}{\sqrt{(\text{Glucose}_{0\text{ min}} \times \text{Insulin}_{0\text{ min}} \times \text{mean Glucose}_{\text{OGTT}} \times \text{mean Insulin}_{\text{OGTT}})}}$$

The homeostatic model assessment of insulin resistance (HOMA-IR) will also be calculated using the formula:

$$\frac{\text{Glucose}_{0\text{ min}} \times \text{Insulin}_{0\text{ min}}}{22.5}$$

Adipose tissue insulin resistance (ADIPO-IR) will be calculated using the formula:

$$\text{Insulin}_{0\text{ min}} \times \text{NEFA}_{0\text{ min}}$$

A one-way repeated measures analysis of variance (ANOVA) will be performed to assess differences in daily energy intake, daily fat intake and 7-day physical activity and sedentary behaviour (i.e sitting time, standing time, light physical activity, moderate-vigorous physical activity) between the high-fat condition, control condition and baseline measurement.

For the outcome measures which will be taken only pre- and post-dietary conditions, a 2×2 repeated measures ANOVA will be used for analysis. This includes the following outcome measures: Body fat percentage, resting metabolic rate, fat oxidation percentage, glucose AUC, insulin AUC and Matsuda ISI.

For the outcome measures which will be taken both pre-diet and post-diet as well as one and three days into the diet, a 2 x 4 repeated measures ANOVA will be used for analysis. This includes fasting plasma concentrations of: LECT2, FGF21, fetuin-A, acylated ghrelin, PYY, CTX, P1MP, glucose, insulin, NEFA and triglycerides. These outcome measures also include: HOMA-IR, ADIPO-IR, subjective ratings of appetite, food preference, body mass and both systolic and diastolic blood pressure.

Where a significant interaction effect is observed, *post hoc* paired samples *t*-tests with a Bonferroni correction will be used to locate any differences. If Mauchly's test of sphericity is violated by any variables, Greenhouse-Geisser corrected values will be used.

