## **OVEREAT Study Protocol**

### *Objective(s)*

The objectives of the present study are as follows:

- To examine the effects of high-fat overfeeding across a 7-day period, on circulating concentrations of the hepatokines LECT2, FGF21 and Fetuin-A.
- To examine the effects of high-fat overfeeding across a 7-day period, on subjective appetite, food preference and circulating concentrations of the appetite regulatory hormones Ghrelin and PYY.
- To observe whether changes in these variables occur alongside impairments in insulin sensitivity and glucose tolerance following seven days of high fat overfeeding.

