of the oral glucose tolerance test. During this, participants will consume a solution

containing 75 g of glucose dissolved in 300 ml of water and further blood samples will be

taken at 0.5, 1, 1.5 and 2 h. The cannula will then be removed and the dietary condition will

commence upon leaving the laboratory. During the 7-day dietary period, participants will

undergo further monitoring of physical activity and sedentary behaviour, while during the

control condition; participants will also complete a 3-day food diary in order to confirm

maintenance of their habitual diet.

Both one day and three days after commencing the diets, participants will return to the

laboratory at 8:00am following a 10-hour overnight fast and having refrained from caffeine,

exercise and alcohol. Further repeat, written informed consent will be and measurements of body weight, blood pressure, subjective appetite and food preference will be obtained. A venous blood sample will then be collected via venepuncture to allow for the assessment of the time-course of changes in fasting circulating hepatokine and appetite hormone concentrations.

Upon completion of the 7-day dietary condition, participants will attend the lab the following morning at 8:00am following a 10-hour overnight fast and having refrained from caffeine, exercise and alcohol. Participants will undergo a post-diet assessment using the same procedures as the pre-diet assessment. A washout period of three weeks will then separate the two dietary conditions.

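### Does the plan need a primary outcome or an adjustment across the three hepatokines?

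*SAP*

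**What the plan says.** The SAP sets one alpha for all analyses: P < 0.05 "will be set to indicate statistical significance". It gives no split or ranking across outcomes.

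The SAP title, "Influence of High-fat Overfeeding on Circulating Hepatokine Concentrations", puts the hepatokines forward as a group. The protocol's Objective(s) section lists three aims without calling any of them primary:
- effects "on circulating concentrations of the hepatokines LECT2, FGF21 and Fetuin-A";
- effects on appetite ratings, food preference and two appetite hormones (PYY and ghrelin);
- "To observe whether changes in these variables occur alongside impairments in insulin sensitivity and glucose tolerance".

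In the SAP the hepatokines stand in one unranked list analysed by 2 x 4 (condition by time) repeated measures ANOVA: "This includes fasting plasma concentrations of: LECT2, FGF21, fetuin-A, acylated ghrelin, PYY, CTX, P1MP, glucose, insulin, NEFA and triglycerides". CTX and P1MP are in that list but in no protocol objective. The list continues with HOMA-IR, ADIPO-IR, appetite ratings, food preference, body mass and blood pressure.

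The one multiplicity provision is in the SAP's closing paragraph. After a significant interaction, paired t-tests "with a Bonferroni correction will be used to locate any differences". That step compares means within one outcome, not across outcomes.

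**The concern.** The title asks about hepatokines collectively, while the plan tests three of them separately at 5% each and does not say how the three results combine. Someone who accepts any one significant interaction as a yes has three chances of a false positive. With no label fixed in advance, the marker put forward as the answer could also be picked once the P values are known. The Bonferroni step does not help, because it starts only after an outcome's interaction is already significant.

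At stake would be a headline that overfeeding alters circulating hepatokines, resting on one of three markers in 12 participants and wrong more often than the nominal 5% suggests.

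**Working it through.** **Inputs.** From the documents: alpha 0.05 per test (SAP); three hepatokines (protocol, Objective(s)); 12 participants in a crossover (protocol, Design); two conditions by four time points (SAP). Not in the documents, so assumed: the correlation between hepatokines (0 to 0.9) and, for the main figures, sphericity. The documents state no power, effect size or familywise error rate, so there is no figure of theirs to reproduce.

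**The test.** The 2 x 4 interaction is equivalent to a one-way repeated measures ANOVA on the condition difference at the four times. Degrees of freedom are 4 - 1 = 3 and (4 - 1) x (12 - 1) = 33.

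**Any-one-counts rule, independent outcomes.** 1 - (1 - 0.05)^3 = 1 - 0.857 = 0.143.

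**Any-one-counts rule, correlated outcomes.** Null simulation of the F(3,33) test on three equicorrelated normal outcomes, 200,000 replicates:

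| Assumed correlation | At least one P < 0.05 | Any false positive with Holm |
|---|---|---|
| 0 | 14.3% | 4.9% |
| 0.3 | 13.9% | 4.9% |
| 0.5 | 12.8% | 4.6% |
| 0.7 | 11.5% | 4.1% |
| 0.8 | 10.3% | 3.7% |
| 0.9 | 8.7% | 3.1% |

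Each single test rejects 4.9-5.1% of the time. A separate simulation of the same test gave 14.0%, 13.0% and 8.8% at correlations 0, 0.5 and 0.9.

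**Effect of the sphericity assumption.** With an assumed AR(1) correlation of 0.7 over the four times, and the SAP's rule of using Greenhouse-Geisser when Mauchly's test is violated, the range becomes about 10-16%. Single tests then reject about 5.7% of the time. That small excess belongs to the individual test, not to having three of them.

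**The other reading.** If each hepatokine is its own question, the error rate for each answer is the single-test rate, about 5%. Nothing is inflated.

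**Cost of controlling the family.** Under F(3,33), a noncentrality of 12.28 gives 80% power at 0.05. The 80% is a reference point only, since the plan states no power. At Holm's first step, 0.05 / 3 = 0.0167, the same noncentrality gives 64.0%, a loss of 80 - 64 = 16 percentage points. By simulation, Holm's power per responding hepatokine is about 64% if one responds, 67-68% if two respond equally and 70-74% if all three do.

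A fixed testing order keeps 80% for the first hepatokine. If that one does not respond and the outcomes are independent, an 80%-power effect in the second is declared only 0.05 x 0.80 = 4% of the time.

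**Which reading fits the text.** The first objective names three analytes. The SAP gives each its own ANOVA, defines no combined hepatokine endpoint and claims no overall error rate. The protocol's reason for the day 1 and day 3 samples is the "assessment of the time-course of changes in fasting circulating hepatokine and appetite hormone concentrations", which is descriptive of each marker. Only the title's collective noun points the other way, and a title is not a decision rule.

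**The case for a change.** The strongest case for a change is that the SAP does not choose between the two readings, its title favours the collective one, and a sentence of SAP text would close the question without touching data collection or models. With 12 participants and no power calculation in the supplied text, one isolated significant marker is easily over-read. The 9-14% counts only the interaction; if a significant condition main effect also counted, the simulated chance would be about 17-26%.

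The arithmetic stands, and so does the observation that no outcome is labelled primary. A conclusion about hepatokines in general drawn from a single marker would carry the inflated error.

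The step from there to a needed change does not stand. That conclusion would be the reader's or author's addition, because the plan neither defines nor licenses it. The room for choosing afterwards is also narrow: the outcomes, their models and the interaction as gate to post hoc testing are all fixed in the SAP, and both title and first objective put the same three markers in front. Holm, a single primary hepatokine and a fixed order would each hold 5%, but each gives something up. Naming the hepatokines as the primary family would also demote the appetite and insulin-sensitivity objectives, which the protocol lists on the same footing.

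**Conclusion.** No change to the plan follows. Carried out as written, it gives a valid answer for each hepatokine at about 5%. The 9-14% arises only if any one of the three is allowed to stand for all; it assumes sphericity and a between-marker correlation from 0.9 down to 0, none of which the documents supply. Familywise control would cost about 16 points of power from an assumed 80% when one hepatokine responds. In a short mechanistic crossover whose aims are to examine and observe, whether to pay that is a judgement for the investigators.

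The absent primary label is missing detail that analysts fill sensibly by reporting all three hepatokines in full and stating that P values are not adjusted across outcomes. One protocol passage was not available and no registry record was seen, so it cannot be said that the trial has no primary outcome, only that the supplied text names none.

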### *Design*

The present study is a randomised, controlled, crossover design in which 12 recreationally active, healthy males will complete two week-long dietary conditions in a randomised order.

The two dietary conditions consist of a high-fat condition and a control condition. In the high-fat condition, participants will consume a diet comprising of 65% of total energy as fat and a total kilocalorie content equal to 150% of their estimated daily requirement. In the

control condition, participants' will consume their habitual diet as confirmed by a three-day food diary both before and during the control condition. The two diets will last seven days each with a three-week washout period separating the two conditions. An oral glucose tolerance test will be performed before and after the two diets to assess glycaemic control and hepatokine and appetite hormone responses will be measured across the seven days.

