### *Methods*

#### Protocol

The participants will firstly undergo a prescreening visit to the laboratory in which written informed consent will be obtained. Further to this, participants will complete a health screen questionnaire, an international physical activity questionnaire and a food preference questionnaire in order to ensure compliance with the eligibility criteria and that the foods provided during the trial will be palatable. Anthropometrical measures will be then be taken including height, weight, waist circumference and body fat percentage (measured via bioelectrical impedance analysis). A finger prick blood sample will also be taken and fasting blood glucose concentrations will be analysed using a Cardiochek device in order to confirm normal fasting blood glucose levels as stated in the eligibility criteria. Prior to completing the prescreening session, participants will be set up with hip-based physical activity monitor (Actigraph) and a thigh-based sedentary behaviour monitor (ActivPAL) and instructed to wear the devices for seven days. Participants will then be provided with an activity diary to record periods where the devices are removed as well as a 3-day food diary (including two

week days and one weekend day) to complete. This will allow for a baseline assessment of the participants' habitual eating and activity habits.

After the completion of the 7-day physical activity and sedentary behaviour monitoring,

participants will be randomised to either the high-fat condition or the control condition.

Participants will attend the laboratory at 8:00 am for a pre-diet assessment following a 10-

hour overnight fast and having refrained from caffeine, exercise and alcohol in the prior 24

hours. Upon arrival, repeated written, informed consent will then be obtained and body

weight, body fat percentage and blood pressure will then be measured. Following this,

participants will be fitted with a mouth piece and their resting metabolic rate and fat

oxidation will be measured via indirect calorimetry using Douglas bags for expired gas

collection. Subjective ratings of appetite will then be measured using visual analogue scales

and food preference will be assessed using computer-based software (Leeds Food

Preference Questionnaire). A cannula will then be inserted into an antecubital vein for blood

sampling. A baseline blood sample (0 h) will be collected, followed by the commencement

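### The planned ANOVAs and t-tests omit period and sequence although diet order is randomised over two periods; adding sequence is a cheap gain in precision

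*SAP*

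**What the plan says.** The protocol's Design section has 12 participants who "will complete two week-long dietary conditions in a randomised order", separated by a three-week washout. The Methods section says that each man is randomised to one of the two conditions after the baseline monitoring week. It gives no ratio, blocking or counterbalancing of order.

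The SAP then names four kinds of test:

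- A one-way repeated measures ANOVA for intake and activity, comparing three levels: "between the high-fat condition, control condition and baseline measurement".
- For the outcomes assessed at two visits per period (Matsuda ISI, OGTT areas for insulin and glucose, fat oxidation, resting metabolic rate and body fat), the SAP's rule reads: "For the outcome measures which will be taken only pre- and post-dietary conditions, a 2×2 repeated measures ANOVA will be used for analysis".
- For the hepatokines, appetite hormones and other four-visit outcomes: "a 2 x 4 repeated measures ANOVA will be used for analysis".
- Bonferroni-corrected paired t-tests, which begin "Where a significant interaction effect is observed". If sphericity fails, "Greenhouse-Geisser corrected values will be used".

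From the outcomes listed, the factors of the 2×2 and 2×4 analyses are condition and time. Period, sequence and order are named nowhere.

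**The concern.** In a two-period crossover, each man's high-fat minus control difference contains the diet effect plus or minus any difference between periods, with the sign set by his diet order. If the analysis ignores order, this does two things. The sign difference between men adds to the error variance, and with unequal sequence groups the part that does not cancel shifts the estimate.

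Whether a given test is exposed depends on the form of the period effect:

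- **The same shift at every visit of a period** cancels from the condition-by-time interaction. It stays in the condition main effect, in any post hoc test comparing conditions at one visit, and in the high-fat versus control part of the one-way ANOVA.
- **A different within-week change in the two periods** goes directly into the interaction.

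The protocol leaves a possible route for the second form. Prescreening is described as "Anthropometrical measures will be then be taken including height, weight, waist circumference and body fat percentage", plus questionnaires, a finger-prick glucose and fitting of activity monitors. Gas collection first appears at the pre-diet visit, where "participants will be fitted with a mouth piece and their resting metabolic rate and fat" oxidation are measured. Blood pressure, the appetite scales and the OGTT also first appear there. A first-exposure effect at that visit would alter the period-1 change only.

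At stake are some power in a trial of 12 and, if the split is unequal, a distortion that readers cannot judge because the split is not promised in the report.

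**Working it through.** **Inputs.** From the documents: n = 12, two periods, two orders, alpha 0.05. The documents give no SD, effect size, period effect, sidedness or randomisation method. Assumed: two-sided tests; an effect of 0.889 SD, which gives the unadjusted test 80% power; and shifts of 0 to 0.8 SD. The unit is the within-sequence SD of the within-person contrast d. There is no stated power figure to reproduce.

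**Model.** Let d be high-fat minus control (for the 2×2 interaction, the difference between the two pre-to-post changes), τ the diet effect and π the period effect. Then E[d] = τ − π when high-fat comes first and τ + π when it comes second. With n1 men high-fat first and n2 control first:

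- Unadjusted mean: bias = π(n2 − n1)/12.
- Unadjusted variance of d: expected value 1 + 4·n1·n2·π²/(12 × 11). At 6:6 and π = 0.5 this is 1 + 144 × 0.25/132 = 1.27, not 1.
- With sequence in the model: no period bias; SE = √[(1/n1 + 1/n2)/4], on 10 df instead of 11 (critical t 2.228 instead of 2.201).

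**At 6:6** (single contrast or 2×2 interaction):

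| Shift (SD) | Power without term | Type I error without term | Power with term |
|---|---|---|---|
| 0 | 80% | 5.0% | 79% |
| 0.25 | 78% | 4.4% | 79% |
| 0.5 | 72% | 3.0% | 79% |
| 0.8 | 59% | 1.3% | 79% |

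Type I error with the term is 5% throughout. The unadjusted estimate is unbiased here, and its test is conservative.

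**At other splits:**

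| Split | Share of π in unadjusted estimate | SE with term | Power with term | Cost if π = 0 |
|---|---|---|---|---|
| 6:6 | 0 | 0.289 | 79% | about 1 point |
| 7:5 | 1/6 | 0.293 | 78% | 2 points |
| 8:4 | 1/3 | 0.306 | 74% | 6 points |
| 9:3 | 1/2 | 0.333 | 67% | 13 points |

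At 8:4 with a 0.5 SD shift the bias is 0.5 × 1/3 = 0.17 SD, and unadjusted power is 87% or 54% depending on direction. At 9:3, unadjusted type I error is about 9% for a 0.5 SD shift and 13% for 0.8 SD.

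**How likely is imbalance?** If allocation were by simple 1:1 randomisation (an assumption), 6:6 has probability C(12,6)/2¹² = 924/4096 = 22.6%, and 8:4 or worse 38.8%.

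**The 2×4 interaction.** At 6:6, the period difference was taken to grow linearly to the stated size at the post-diet visit, with adjacent-visit correlation from 0 to 0.7. Power without the term is 79–80% at 0.25 SD, 75–78% at 0.5 SD and 66–75% at 0.8 SD. With sequence it is 79–80%.

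**Does the amended 2×4 ANOVA hold its level?** In null simulations at 6:6 over the same correlations, with Greenhouse-Geisser applied when Mauchly's test is significant, type I error is 5.0–5.7% with sequence and 4.9–5.7% without it. Adding the factor does not disturb the planned sphericity protection.

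**The case against.** The case for leaving the plan alone has real force.

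- **The gating test is largely protected.** Each period has its own pre-diet visit, and post hoc tests follow only a significant interaction. A reader might infer that the missing term undermines the hepatokine results. The documents do not support that: a level shift cancels, and a period difference in change of up to 0.5 SD costs the 2×4 test only a few points of power. This stands.
- **The exposed tests are thinly specified.** The SAP does not make the condition main effect a basis for conclusions, does not say which pairs the post hoc tests compare, and plans a three-level F-test, not a separate high-fat versus control test. This stands. It limits the weight of the point but does not remove it.
- **No period effect is documented.** For the 2×2 interaction with independent visit errors, SD(d) is twice the single-visit SD, so a 0.5 SD shift needs a first-visit effect of one full single-visit SD. That is speculative for OGTT measures, and body fat is already measured at prescreening. This stands.
- **The term can lose power.** It gains only above shifts of about 0.16 SD at 6:6, 0.24 at 7:5 and 0.37 at 8:4. Averaged over simple randomisation, power is 75% with the term. Without it, power is 80% at no shift, 75% at 0.35 SD and 71% at 0.5 SD. This argues for blocking, and for stating the cost openly. It does not argue for leaving the term out at very unequal splits, where the bias is largest.

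A reader might also infer that the baseline week should leave the formal analysis because it always comes first. That does not follow. If activity moves after baseline, the three-level F-test is detecting a departure from habit, which the Diet section of the protocol wants checked. Reading a non-significant result as proof of unchanged habits is a separate problem, which a period term does not cure.

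Nor may one infer that the order was in fact unbalanced, or that the plan is biased on average. The documents are silent on balance, and over simple randomisation the imbalance averages out. The shift concerns only the realised split.

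**Conclusion.** The omission is real: order is randomised, no analysis accounts for it, and balance is not stated. It is a low-cost precision improvement, not an error that invalidates the interaction tests.

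At 6:6 the consequence is conservative testing, about 8 power points lost against the unshifted 80% if the shift is 0.5 SD, with no bias. At unequal splits the realised estimate also carries one sixth (7:5), one third (8:4) or one half (9:3) of the period effect, and false positives rise clearly only at the extreme splits. All these sizes rest on assumed shifts, an assumed effect of 0.89 SD and two-sided tests. That no term is specified rests on the text alone.

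**What to change.** 1. Keep the planned 2×2 and 2×4 repeated measures ANOVAs with Greenhouse-Geisser correction. Add sequence (diet order) as a between-subject factor with Type III sums of squares, at every realised split. The condition effect is then the equally weighted average of the two sequence groups.
2. For any single high-fat versus control contrast, regress the within-person difference on sequence coded −1/+1 and test the intercept on 10 df. This covers between-condition post hoc tests (keeping Bonferroni) and the intake and activity comparison.
3. If allocation is still open, block the order 6:6. In either case report the realised split.
4. If the split is more unequal than 7:5, report the unadjusted analysis alongside as a sensitivity analysis. The adjusted one stays primary.
5. Keep the planned comparison with the baseline week, and note that it always comes first and cannot be period-adjusted.

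The cost is a few lines of SAP text, one extra factor in the planned SPSS procedure and one degree of freedom per contrast. The power cost when there is no period effect is in the second table above: small at 6:6 and 7:5, and material at 8:4 and beyond. That is the reason to block if it is still possible.

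### The planned repeated measures ANOVAs drop a participant from an outcome if any one of his eight (or four) values is missing, and the plan has no missing-data rule

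*SAP*

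**What the plan says.** The Protocol (Design) has "12 recreationally active, healthy males will complete two week-long dietary conditions in a randomised order". Each condition has a pre-diet and a post-diet assessment. In between, the Protocol (Methods, Protocol) adds two fasted visits: "Both one day and three days after commencing the diets, participants will return to the" laboratory. That makes four visits per condition and eight per man.

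The SAP sorts outcomes by schedule:

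- Outcomes "taken both pre-diet and post-diet as well as one and three days into the diet" go to a 2 × 4 analysis: "a 2 x 4 repeated measures ANOVA will be used for analysis". The list begins: "This includes fasting plasma concentrations of: LECT2, FGF21, fetuin-A, acylated ghrelin, PYY, CTX, P1MP, glucose, insulin, NEFA and triglycerides". It continues with HOMA-IR, ADIPO-IR, appetite ratings, food preference, body mass and blood pressure. These cover the first two objectives.
- Body fat, resting metabolic rate, fat oxidation, glucose and insulin AUC and Matsuda ISI are "taken only pre- and post-dietary conditions, a 2×2 repeated measures ANOVA will be used for analysis".

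The SAP provides for non-normality, non-sphericity and post hoc multiplicity. Neither document has a missing-data rule, a replacement rule, a dropout allowance or a definition of the analysis population.

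**The concern.** A classical repeated measures ANOVA needs a full row of values from each person. If one cell of the 2 × 4 layout is empty, the other seven are discarded for that outcome. With 12 men, each deletion costs 1/12, about 8% of the sample.

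How far a loss spreads depends on its cause:

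- A failed assay affects that analyte and anything computed from it. Fasting insulin, for example, feeds HOMA-IR and ADIPO-IR.
- A missed visit affects every outcome due at that visit.
- A man who completes only period 1 contributes to no 2 × 2 or 2 × 4 analysis.

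Some loss is plausible. The schedule asks for eight fasted 8:00 am attendances with blood sampling, a three-week washout and a week of substantial overfeeding. Acylated ghrelin also needs its own pre-treated and re-spun tube. If stopping relates to tolerance of the high-fat week, the complete cases are also a selected group.

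**Working it through.** **Inputs.** From the documents: 12 men and 2 conditions (Protocol, Design); 4 time points or 2 time points according to outcome (SAP). There is no missing rate, SD, effect size or sample-size calculation, so there is no figure of the plan's own to reproduce. The missing rates and variance components below are assumptions.

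**1. One missing value.** A 2 × 4 outcome has 12 × 8 = 96 cells. With one missing, 95 values are observed. The ANOVA keeps 11 × 8 = 88 of them and discards 7. Error degrees of freedom fall from 11 to 10 for condition and from 33 to 30 for the interaction. A mixed model uses all 95 values and all 12 men.

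**2. Expected complete men.** Let m be the missing rate per visit, independent across visits. A man is complete with probability (1 − m)^8 for a 2 × 4 outcome and (1 − m)^4 for a 2 × 2 outcome; multiply by 12. The chance of losing at least one man is 1 − (1 − m)^96 or 1 − (1 − m)^48.

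| m | (1 − m)^8 | Complete, 2 × 4 | Lose ≥ 1 | (1 − m)^4 | Complete, 2 × 2 | Lose ≥ 1 |
|---|---|---|---|---|---|---|
| 1% | 0.923 | 11.1 | 62% | 0.961 | 11.5 | 38% |
| 2% | 0.851 | 10.2 | 86% | 0.922 | 11.1 | 62% |
| 5% | 0.663 | 8.0 | 99% | 0.815 | 9.8 | 91% |

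**3. Precision, 2 × 4 outcomes.** The contrast is the pre-to-post change on the high-fat diet minus that on control. With complete cases its variance is proportional to 1/n. At the expected n, the standard error ratio is √(12/10.21) = 1.08 at 2% and √(12/7.96) = 1.23 at 5%. Because n itself varies, averaging over its binomial distribution raises these to about 1.09 and 1.25.

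For all available visits I simulated missing patterns and computed the generalised least squares variance, with the covariance treated as known and the residual variance set to 1. The ratio was about 1.01 at 2% and 1.03 at 5% with participant variance only. With participant-by-condition and participant-by-visit variances of about 0.5 each, it was about 1.02 and 1.05. Larger interaction variances took the 5% figure to about 1.06.

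**4. Power, as illustration only.** Take a single paired contrast with 80% power at n = 12 (two-sided 0.05, standardised effect 0.89, solved for that purpose). Its power is 76% at n = 11, 71% at n = 10 and 58% at n = 8.

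**5. Which mixed model.** Suppose data are complete, there is no true effect, the residual SD is 1 and the participant-by-condition SD is 0.7 (variance 0.49). The correct error mean square for condition has expectation 1 + 4 × 0.49 = 2.96. A model with a participant intercept only pools all within-person error over 11 + 33 + 33 = 77 df, giving (11 × 2.96 + 66 × 1)/77 = 1.28. The condition test is then inflated by 2.96/1.28 = 2.31, and the interaction test is deflated by 1/1.28 = 0.78. By simulation, the condition test rejects about 19–20% of the time and the interaction test about 2%, at a nominal 5%. The planned ANOVA's interaction test stays at about 5%.

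**The case against.** The SAP nowhere orders deletion. It follows from the named method, and imputation is neither planned nor excluded. One sentence on missing data would fill the formal gap. If all eight visits succeed for every man, nothing is lost.

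The sizes depend on assumed rates. At 1%, 11.1 of 12 men remain; the largest losses belong to the 5% end. Independence is pessimistic: if missed visits cluster in the same men, fewer men are lost for the same average rate. The power figures concern one paired contrast, not the 2 × 4 interaction test. The precision figures for all available visits treat the covariance as known, which favours the mixed model somewhat.

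A reader might infer that one failed sample removes a man from the whole trial. The documents do not support that. Outcomes are analysed separately, so a failed LECT2 assay affects LECT2 alone. A missed day 1 or day 3 visit leaves the 2 × 2 outcomes untouched. Each post hoc paired t-test needs only its own two values, although those tests are reached only after a significant interaction in the reduced set.

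A reader might also infer that a mixed model removes bias from selective dropout. It does so only if data are missing at random given what was recorded. Dropout driven by unrecorded intolerance of the diet would bias both analyses.

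These points limit the scope and size. They do not alter the fact that the named method discards observed data and the plan has no rule to prevent it.

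**Conclusion.** The concern holds, outcome by outcome. The analyses named for the hepatokine and appetite objectives need eight values per man, and the pre/post analyses need four. If visits are missed independently at 1–5%, a 2 × 4 outcome can expect to lose about one to four of its 12 men. At 2–5%, its standard error rises by about 9–25%, most of which is avoidable with data already collected.

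The need for complete records follows from the method and rests on no assumed rate; only the size does. The documents do not allow a prediction of how many men will actually be lost. This should be corrected before the analysis, but it does not invalidate the design.

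**What to change.** Replace the 2 × 2 and 2 × 4 ANOVAs with a linear mixed model for each outcome in SPSS MIXED (REML, Satterthwaite degrees of freedom), using every available value:

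- **Fixed effects:** condition, visit, condition × visit and period. Period is needed because records from one period only would otherwise bring period differences into the condition comparison.
- **Random effects:** participant, participant-by-condition and participant-by-visit, so that the model has the ANOVA's error strata. A participant intercept alone is not adequate (step 5 of the working).
- **Reporting:** the number of participants and of values analysed for each outcome, with reasons for missing values.
- **Sensitivity analysis:** the complete-case ANOVA with the Greenhouse-Geisser correction.

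The cost is a few lines of SAP text and syntax in the same software, with no new data. The covariance structure must be fixed in advance, including what will be done if a variance component is estimated at zero or the model fails to converge, which is a real possibility with 12 men. The missing-at-random assumption should be stated, together with its limit for dropout linked to unrecorded intolerance of the diet.
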